We anticipate low, but potentially important rates of survey non-response to all or part of the 6- and 12-month surveys. We will use the evidence-based recruitment strategies described above (incentives, reminders, mixed mode survey administration) to minimize non-response. A common practice in smoking cessation research is to treat non-respondents at follow-up as continuing smokers (i.e., intent to treat). This practice is perceived to be a conservative approach but does not, in fact, produce valid estimates of quit rates.³³ We will use multiple imputations to fully use available baseline information and partial later surveys. We will use a propensity-based multiple imputation method similar to that discussed by Little³⁴ using separate imputation procedures within each study group and design stratum combination. Within a given combination, we will estimate the propensity for responding to cotinine validated abstinence for each individual from a logistic regression model for survey response using the characteristics measured at baseline as explanatory measures. Within a combination of intervention and design strata, we will further stratify the sample according to the values for these estimated propensities. Within a propensity substratum, we will impute a value for the outcome measure for each non-respondent by randomly sampling an outcome value from the respondent values in the substratum. Multiple completed datasets will be created and the point estimates and the estimated standard error from each dataset will be combined to arrive at a single point estimate (using the specific method discussed below), its estimated standard error, and the associated confidence interval or significance test. This approach assumes that missing outcome data due to non-response is missing at random.

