The power analysis is based on the primary outcome – cotinine-validated abstinence at 12-month follow-up. Our data is stratified on four hospital sites. Considering that a stratified random sample is usually more efficient than a simple random sample, to be conservative, we assume the two groups are two independent simple random samples in the following power analysis. Based on response rates during the first quarter of recruitment, we expect to receive completed surveys from 20-25% of the 20,000 patients receiving the initial mailing and 85% of respondents will be eligible (i.e., report smoking cigarettes in the prior 30 days). We will send initial mailings until we receive completed surveys from 3,840 eligible patients who will be randomly assigned to intervention and control and comprise the study population. We estimate the quit rate in the control group will be 4%. In the intervention group, about 20% of the people will accept our offer of telephone treatment, based on [name] data. We anticipate that the quit rate among Veterans

enrolled in counseling will be 16%. We are using a more conservative estimate from what we found in our recently-completed reactive recruitment study (20%) because participants will not have been directly referred from a healthcare provider. When the treatment cessation rate is combined with that from patients who do not accept treatment (assuming also a 4% quit rate), there will be a population-level quit rate of 6.4% in the intervention group, which gives us a 90% chance to detect a difference between the two groups.

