The table below shows the detectable increases in anticipated long-term abstinence rate for the intervention group for power = 0.75, 0.80, 0.85, 0.90, based on two sided two independent proportions test with type I error of $\alpha=0.05$. We varied the anticipated long-term abstinence rate in the control group from 3% to 4%. (We used Pass 2008 NCSS software for the calculation.) As an example, the proposed sample size provides 80% power to detect any increase greater than 2.0% in population-level abstinence rate for the intervention group when the abstinence rate in the control group is 4%, a small but clinically-meaningful quit rate that results in overall cost-savings.³⁸ Reversing the calculation and solving for the quit rate for people who accept counseling, if the underlying quit rate is 4% and we get 20% of intervention patients to enroll in counseling (N=384), we will have 80% power to detect a difference if the success rate at counseling is as low as 14%.

Note that a lower response rate on the baseline survey does not affect our power. Since we randomize after response, we can mail additional surveys until we have 3,840 respondents. A recruitment cohort of 20,000 patients and enrolled sample of 3,840 participants therefore gives us some safety margin, to allow for variability in:

- The treatment engagement rate
- The rate of success at counseling (i.e., if less than 16%)
- If the success rate among intervention patients who do not enroll in counseling is <4% (which is conceivable, since these are the people who declined to enroll in telephone counseling).

Table 1: Statistical Power Analysis (1920 baseline survey respondents per group) for Abstinence Rates

| Control group P1 | Power | Intervention group P2 | Difference P2-P1 | Odds Ratio |
|------------------|-------|-----------------------|------------------|------------|
| 0.03 | 0.95 | 0.053 | 0.023 | 1.82 |
| 0.03 | 0.90 | 0.051 | 0.021 | 1.72 |
| 0.03 | 0.85 | 0.049 | 0.019 | 1.66 |
| 0.03 | 0.80 | 0.047 | 0.017 | 1.61 |
| 0.03 | 0.75 | 0.046 | 0.016 | 1.57 |
| 0.04 | 0.95 | 0.066 | 0.026 | 1.70 |
| 0.04 | 0.90 | 0.063 | 0.023 | 1.62 |
| 0.04 | 0.85 | 0.061 | 0.021 | 1.56 |
| 0.04 | 0.80 | 0.060 | 0.020 | 1.52 |
| 0.04 | 0.75 | 0.058 | 0.018 | 1.49 |

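### The hot-deck rule as written gives self-reported quitters with unreturned saliva kits mostly smokers' outcomes; separately, the power figures leave out 12-month outcome loss

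*Combined protocol and SAP*

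**What the plan says.** **Imputation.** Section 6.0, Missing Data, says: "We anticipate low, but potentially important rates of survey non-response to all or part of the 6- and 12-month surveys". It declines to count non-respondents as smokers and uses multiple imputation. Within each arm and design stratum, a logistic model on baseline characteristics gives a response propensity. Participants are grouped by that propensity, and each missing outcome is drawn at random from the respondents in the same group. The section makes clear that the method covers missing cotinine results as well as missing surveys. It also speaks generally of using partly completed later surveys.

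**Saliva.** Section 5.7.4 sends a kit only to people who report 7-day abstinence from cigarettes, other tobacco products, e-cigarettes and NRT.

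**Power.** Section 6.0, Power calculations, expects 4% in control and a "population-level quit rate of 6.4% in the intervention group, which gives us a 90% chance to detect a difference between the two groups". It adds that "the proposed sample size provides 80% power to detect any increase greater than 2.0" percentage points, and that "we will have 80% power to detect a difference if the success rate at counseling is as low as 14" percent. Table 1 is headed "Statistical Power Analysis (1920 baseline survey respondents per group) for Abstinence Rates". On response it says: "Note that a lower response rate on the baseline survey does not affect our power". The "enrolled sample of 3,840 participants therefore gives us some safety margin, to allow for variability in" treatment engagement, counselling success and success among those who decline counselling. Loss of 12-month outcomes is not on that list.

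**The concern.** **Main point: the donor pool.** A cotinine result can be missing in two ways. Someone may not answer the 12-month survey, in which case little is known beyond baseline. Or someone may answer, report abstinence and not return the kit, in which case the most informative predictor has been observed. The stated rule treats both alike. In a substratum built on baseline data most respondents are smokers, so the second person is nearly always imputed as a smoker. The rule is then close to counting an unreturned kit as smoking, a convention of the kind the same section rejects as not giving valid quit rates. What is at stake is bias in the primary estimate.

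**Secondary point: the power basis.** Every power figure uses all 1,920 randomised per arm, as if each had a known 12-month outcome. The section on missing data expects otherwise, gives no rate, and the power section makes no allowance. These figures are the stated case for 3,840 participants.

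**Working it through.** **1. Reproduce the plan's figures.** Inputs from section 6.0: 1,920 per arm, two-sided 0.05, control 4%, intervention 0.20 × 16% + 0.80 × 4% = 6.4%. With pooled variance under the null,

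power = Φ{[p2 − p1 − 1.96·√(2p̄(1 − p̄)/n)] / √[(p1(1 − p1) + p2(1 − p2))/n]}, where p̄ = (p1 + p2)/2.

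- 4% vs 6.4%: 91.8% (stated 90%).
- 4% vs 6.0%: 81.2% (stated 80%).
- Increase detectable with 80% power: 1.97 points (stated 2.0).
- Counselling success needed: (5.967% − 0.8 × 4%)/0.2 = 13.8% (stated 14%).
- All ten rows of Table 1 also reproduce at n = 1,920.

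**2. Donor rule as written.** Let p be the true validated rate, k the share of self-reported abstainers whom cotinine would confirm, and r the share of kits not returned. The documents give neither k nor r. Assume k = 0.70 and r = 0.20, equal by arm, with no other missing data and baseline variables that do not predict the outcome. The share reporting abstinence is p/k. Respondents make up 1 − r·p/k of the arm, and validated abstainers among them (1 − r)p. Drawing the rest from respondents gives

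estimated rate = (1 − r)p / (1 − r·p/k).

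- Control: 0.8 × 0.04 / (1 − 0.2 × 0.04/0.7) = 0.0320/0.9886 = 3.24%.
- Intervention: 0.8 × 0.064 / (1 − 0.2 × 0.064/0.7) = 0.0512/0.9817 = 5.22%.

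In people, for control: 1,920 × 0.04/0.7 ≈ 110 report abstinence and about 22 return no kit. About 0.7 × 22 ≈ 15 of those are truly abstinent, but the rule credits about 22 × 3.24% ≈ 0.7.

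The difference shrinks from 2.4 to 1.98 points. The ratio barely moves (5.22/3.24 = 1.61 against 1.60). Power is 86.2% at the full 1,920 and 85.7% after allowing for the missing results, so the loss is almost all bias. The estimates hardly depend on k: with r = 0.20, k = 0.5 gives 3.25% vs 5.25% and k = 0.9 gives 3.23% vs 5.19%.

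**3. Restricted donors.** Donors are self-reported abstainers in the same arm and site who returned a sample. Simulation (hot-deck with 20 imputations, Mantel-Haenszel log odds ratio pooled by Rubin's rules), k = 0.70:

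| Kits unreturned | Rule as written: rates | Power | Restricted donors: rates | Power |
|---|---|---|---|---|
| 10% | 3.62 vs 5.82% | 89.4% | 4.0 vs 6.4% | 91.3% |
| 20% | 3.24 vs 5.21% | 85.4% | 4.0 vs 6.4% | 89.7% |
| 30% | 2.85 vs 4.60% | 81.8% | 4.0 vs 6.4% | 88.4% |

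**4. Power with missing 12-month outcomes.** Let m be the share missing (assumed). Three cases:

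- Imputation recovers little: n = 1,920(1 − m).
- Predictors explain 25% of outcome variance: n = 1,920/[1 + 0.75m/(1 − m)].
- Planning rates already count non-respondents as smokers: rates p/(1 − m) with n = 1,920(1 − m).

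Power for 4 vs 6.4% / 4 vs 6.0%:

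| Missing | Little recovered | 25% explained | Non-respondents already counted as smokers |
|---|---|---|---|
| 0% | 91.8 / 81.2 | 91.8 / 81.2 | 91.8 / 81.2 |
| 5% | 90.4 / 79.2 | 90.8 / 79.7 | not tabulated |
| 10% | 88.9 / 77.0 | 89.6 / 78.0 | 92.0 / 81.4 |
| 20% | 85.0 / 72.0 | 86.8 / 74.2 | 92.1 / 81.7 |

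In the first case, 90% needs 1,797 per arm (1 − 1,797/1,920 = 6.4% missing) and 80% needs 1,863 (3.0% missing). At 5, 10 and 20% missing the detectable increase is 2.02, 2.08 and 2.23 points, and the counselling success needed is 14.1, 14.4 and 15.1%.

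**The case against.** **On the donor rule.** The plan mentions partial later surveys, so the statisticians may intend to use the self-report. It also plans pattern-mixture analyses that cover missing cotinine results. The first part stands as a reason to ask for the rule in writing; the operational steps, however, name only baseline characteristics. The second part does not change the primary rule, because those analyses assess sensitivity around it. The sizes rest on assumed kit return and confirmation, and a reminder schedule with a second kit and a payment (section 5.7.4) may keep unreturned kits few. That stands too.

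**On power.** No stated figure is wrong, and Table 1 is open about its basis. The only guidance on missingness is that it will be low. At 5% missing the 90% statement still holds, the 80% statement is short by under one point, and 2.0 and 14% are unchanged at the precision printed. Up to ten calls followed by a mailed survey (section 5.7) support good completeness. The 16% counselling success is itself cautious: at the earlier study's 20% (0.20 × 20% + 0.80 × 4% = 7.2% overall), power is 97.1% even with 20% missing. All of this stands and limits the weight of the secondary point. The cut-offs also depend on the test. The plan names exact methods, and an unstratified Fisher test gives 91.0% and 79.5% with complete data.

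**Stronger readings.** A reader might infer that the power arithmetic is wrong or that the trial is underpowered. The documents support neither: the figures reproduce, no missing-data rate is given, and the basis of the planning rates is not stated. Nor does the donor rule favour the intervention. With equal return by arm it lowers both rates and narrows the difference.

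**Conclusion.** The main point holds. Followed as written, the imputation rule disregards an observed self-report and biases the primary abstinence rate downward in both arms. At the assumed 20% unreturned and 70% confirmed, the estimates are about 3.2% and 5.2% in place of 4.0% and 6.4%, and power is about 86% against about 90% with restricted donors. The direction follows from the text alone; the size depends mainly on kit return.

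The secondary point holds as an omitted planning assumption. The 90% statement is safe to about 6.4% missing and the 80% statement to about 3.0%, provided that 4%, 6.4% and 6.0% are true rates among all participants and imputation recovers little. The effect is small if missingness is low, and absent if the planning rates already count non-respondents as smokers. The documents do not say which case applies.

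**What to change.** 1. **Section 6.0, Missing Data.** For a self-reported abstainer who was sent a kit and returned no sample, draw donors only from self-reported abstainers in the same arm and site stratum who returned one. Keep the baseline-propensity hot-deck for participants with no 12-month survey.
2. **Section 6.0, Power calculations.** State that the 90% and 80% figures, the 2.0 points, the 14% and Table 1 assume complete 12-month outcomes, or restate them at the expected survey completeness and kit return. Say whether the planning rates count non-respondents as smokers. Add 12-month outcome loss to the safety-margin list.

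**Cost.** Wording, possibly a recalculated table, and a little more analysis work. The restricted donor pool is small: in control, about 0.8 × 110 = 88 returned samples, or about 22 per site if the four sites are equal. Propensity substrata may therefore need to be collapsed. The stated power may look slightly less favourable. No extra patients are needed.

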7.0 WITHDRAWAL OF SUBJECTS

Participants can withdraw from the study at any time verbally or in writing by contacting one of the Principal Investigators. Any data collected prior to the participant's withdrawal will still be

used, but no further data collection or contact with the participant will occur after the date of their withdrawal.

8.0 SAFETY MONITORING AND REPORTING

Potential Risks

The intervention treatment being delivered in this study (counseling) is already shown to be effective and approved by the VA for use without informed consent. The main risk in this study is a breach of confidentiality similar to the risk incurred during a normal visit for care.

Surveillance and Reporting Procedures

In order to ensure patient safety, we will use the same approach we are using for our ongoing VA studies. We will monitor the following events:

Adverse events (AEs):

- Violations of confidentiality
- ER visits without hospitalization
- Suicidal ideation not requiring intervention

Serious adverse events (SAEs):

- Death
- Life-threatening event
- Hospitalization
- Suicidal ideation requiring intervention

Any AE that the research staff thinks may be related to study participation will be reported to a PI within 24 hours. If the PI is unavailable, the research staff will report it to the Project Director. The PI or Project Director will determine whether the event is a) serious or non-serious and b) anticipated or unanticipated. The PI or Project Director will ensure that any necessary actions are taken immediately to address the current patient situation, and then will decide if the team needs to make any changes in the protocol and/or consent forms to prevent future occurrences or better inform future participants. We will report the event to the IRB and DSMB as per VHA Handbook 1058.01 requirements.

In the case of suicidal or homicidal ideation, we will follow a protocol used on previous studies. We will train each person who contacts participants (tobacco cessation counselors and research assistants) in appropriate methods for assessing risk, conversing with participants, and completing a 'warm-transfer' to the VA National Suicide Prevention Hotline if a patient reports suicidal or homicidal ideation, plan or intent during counseling or a telephone survey. Clinicians (either [name], a VA primary care physician, or the counseling supervisor, [name], a VA clinical psychologist) will also be informed to evaluate cases and provide any further advisement or follow-up with patients' primary mental health providers.

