5.5 RANDOMIZATION AND BLINDING

After returning the baseline survey, we will randomize respondents in a 1:1 fashion to intervention or control, stratified by site. To randomize a patient, the Project Director will log onto the study's database system (which will be adapted from the one used in [name] previous studies), enter the subject's unique study ID, confirm eligibility, and confirm that the survey has been received. The database system verifies that all randomization criteria have been satisfied, then assigns a study ID and a group to the subject. The database system will automatically input the date of randomization and the participant's assignment into their study record. The study's Project Director and counselors will have access to treatment assignments. The study's research assistants and our biochemical validation company (Salimetrics, described in section 4.0) will be kept blind to treatment assignments. Intervention participants will be aware of the arm to which they are assigned when they receive the first phone call from a study counselor.

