10.0 COMMUNICATION PLAN

The Project Director will work with the local site coordinators to develop their local IRB applications and ensure that they receive appropriate approvals before beginning research at any site.

Hard copies of all current study materials (e.g., outreach letters, surveys) will be stored on a VA network server to which all study staff will have access to ensure that only the most recent, IRB-approved documents are used. The verbal informed consent process for enrollment in telephone counseling and all telephone surveys will be completed using computer-assisted script and interview programs to ensure that staff are delivering informed consent information and obtaining survey answers in a standardized, IRB-approved methods.

We will have bi-weekly study meetings at our primary site (NY Harbor) and monthly conference calls with all sites to discuss overall study progress, protocols, and updates. When protocol changes, unanticipated problems, and SAEs occur, the Project Director will immediately notify the LSIs and their appropriate staff via phone and schedule a conference call as soon as possible to discuss the events or changes with all sites. Minutes from each meeting and conference call will be emailed to all study staff and stored on a VA server to which all study staff will have access.

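### Listed SAEs other than suicidal ideation that research staff think unrelated have no written route to the PI or DSMB, and no SAE comparison by arm is planned

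*Combined protocol and SAP*

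**What the plan says.** Section 8.0 opens its surveillance text with "We will monitor the following events". The AE list covers confidentiality violations, ER visits without hospitalization, and suicidal ideation that needs no intervention. The SAE list covers death, life-threatening events, hospitalization, and suicidal ideation that does need intervention. Neither list depends on arm or cause.

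The reporting chain then has three steps:

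1. "Any AE that the research staff thinks may be related to study participation will be reported to a PI within 24 hours". The Project Director receives the report if the PI is unavailable.
2. "The PI or Project Director will determine whether the event is a) serious or non-serious and b) anticipated or unanticipated".
3. "We will report the event to the IRB and DSMB as per VHA Handbook 1058.01 requirements".

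Two other texts carry no relatedness condition:

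- **Ideation (section 8.0).** A hotline transfer is made "if a patient reports suicidal or homicidal ideation, plan or intent during counseling or a telephone survey". A study physician or clinical psychologist "will also be informed to evaluate cases and provide any further advisement or follow-up".
- **Communication plan (section 10.0).** "When protocol changes, unanticipated problems, and SAEs occur, the Project Director will immediately notify the LSIs and their appropriate staff via phone".

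On blinding, section 5.5 says "The study's Project Director and counselors will have access to treatment assignments". Research assistants are kept blind.

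**The concern.** The first decision on an event is an opinion about cause, held by whoever hears of it. Section 8.0 does not define research staff. The natural reading takes in counselors, who know the arm, as well as research assistants, who do not. The second step assigns seriousness and expectedness but not relatedness, so no later reviewer is assigned to revisit the staff opinion.

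This matters in a mental health population. A psychiatric hospitalization after a quit attempt can seldom be told from the background course of illness in a single case. An excess shows only when rates are compared between arms. If each case can stop at a staff judgement, and no one tabulates all cases by arm, the DSMB has no stated means of seeing such an excess, or of recognizing that a cluster of reported cases is only background.

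**Working it through.** The plan states no SAE rate and no safety figure, so there is no figure of its own to reproduce on this point. The check is mainly one of text, with a small calculation on opportunity to hear of events.

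**1. Follow one event through section 8.0.** Take a hospitalization that staff learn of and think unrelated.
- Step 1 sends up only AEs thought possibly related, so this event is not sent.
- Step 2 (seriousness) is applied to what step 1 passed, so being on the SAE list does not rescue it.
- Step 3 reports the event already passed up. The VHA handbook may be broader, but it cannot act on an event the PI never received.
- The ideation pathway does not apply.

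**2. Set section 8.0 beside section 10.0.** Section 10.0 assumes that the Project Director knows when SAEs occur. Under section 8.0 the Project Director is only the fallback recipient, and only for events staff think may be related. Either there is an unwritten route for all SAEs, or section 10.0 covers only the filtered ones. The text does not say which.

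**3. Look for a backstop.**
- Section 5.7.5 draws mental health visit counts and prior diagnoses from the EMR. It does not mention deaths, hospitalizations or ER visits.
- The measures listed in section 5.7 include no hospitalization or ER item.
- Section 6.0 contains no safety tabulation by arm.

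**4. Planned live contact by arm.** Inputs: telephone surveys at 6 and 12 months in both arms (section 5.7); 8 counseling calls, then monthly calls for six months for those who quit (section 5.6); 20% counseling uptake and 1,920 per arm (section 6.0).
- Counseled participants: 0.20 × 1,920 = 384, as the plan states.
- Control: 2 calls.
- Counseled participant: 2 + 8 = 10 calls, up to 2 + 8 + 6 = 16.
- Intervention-arm average, no maintenance calls: 2 + 0.20 × 8 = 3.6.
- Intervention-arm average, all counseled participants get six: 2 + 0.20 × 14 = 4.8.
- Ratio to control: 3.6/2 = 1.8 to 4.8/2 = 2.4.

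This assumes that all scheduled calls take place. It leaves out outreach attempts and the mailed surveys.

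**5. Can the imbalance be sized?** That needs an SAE rate, the share staff hear of, and the share they call related. The documents give none of these. As an illustration, assume 10–20% are hospitalized in 12 months and staff call 5–20% of those events related.
- If only the 384 counseled participants come to notice: 0.05 × 0.10 × 384 ≈ 2, up to 0.20 × 0.20 × 384 ≈ 15 reported cases.
- If all 1,920 in the arm do: 0.05 × 0.10 × 1,920 ≈ 10, up to 0.20 × 0.20 × 1,920 ≈ 77.

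A range of 2 to 77 reflects the assumptions and little else. There is no basis for a corresponding control figure.

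**The case against.** The strongest reply is that the text is less restrictive than it looks. The list of monitored events is unqualified. The quoted sentence sets a 24-hour route with a low threshold, and it does not say that other events are discarded. Section 10.0 implies that SAEs do reach the Project Director. What the DSMB receives is governed by a handbook outside these documents.

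Several parts of this stand:

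- **Control events.** The rule applies to both arms. A reader might infer that control SAEs are dropped because that arm received only a mailed list, but nothing excludes them. The research assistants who survey both arms are meant to be blind, so they should not be reasoning from the arm.
- **Clinician review.** A reader might infer that no clinician sees an event staff think unrelated. That is wrong for suicidal ideation reported in counseling or a telephone survey, which reaches a clinician in either arm.
- **Other comparisons.** The Kessler-6 and the Hospital Anxiety and Depression Scale are repeated at 6 and 12 months, mental health distress is a secondary outcome (section 5.8), and mental health visits are counted. A randomized comparison of worsening distress is therefore available. It is not a count of deaths or hospitalizations, and the scales depend on survey response.
- **Unequal ascertainment.** A table by arm of whatever staff happen to hear would carry its own bias, given 10 to 16 planned calls for a counseled participant against 2 for a control. Equal true rates could look like an intervention excess.

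The reply does not supply a written route for an SAE judged unrelated, and it does not reconcile section 10.0 with section 8.0.

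**Conclusion.** The gap holds in a limited form. Followed as written, section 8.0 gives listed SAEs other than suicidal ideation no path to the PI, and so none to the IRB or DSMB, when staff think them unrelated. That judgement comes before seriousness is assessed and may be made by unblinded counselors. No SAE comparison by arm is specified, and sections 8.0 and 10.0 disagree.

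A reader might go further and conclude that the DSMB will see almost only intervention cases. The documents do not support that as a finding. Unequal contact and unblinded counselors make some imbalance plausible, but its size and even its direction depend on rates and staff behavior that are not given. The conclusion rests on the wording alone and on reading research staff to include counselors. If that term means only the blinded research assistants, the missing route remains, but the unblinded filter does not. The text should be amended. The primary efficacy analysis is not affected.

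**What to change.** 1. **Reword section 8.0.** Every listed SAE that staff learn of, in either arm, is logged with its date and sent to the PI within the existing 24 hours, whatever staff think of its cause.
2. **Move the relatedness judgement.** The PI or the study clinicians already designated in section 8.0 assign it, not the reporting staff, and without arm information where feasible. A report from a counselor reveals the arm, so it would need a summary with the counseling details removed.
3. **Reconcile sections 8.0 and 10.0** so that both describe the same set of SAEs and state how the Project Director learns of them.
4. **Keep expedited IRB and DSMB reporting as it is.** Add to the DSMB reports cumulative SAE counts by arm over the number randomized.
5. **Base those counts on sources that are the same in both arms.** These are a short item in the 6- and 12-month surveys run by blinded research assistants, and an EMR extract of deaths, hospitalizations and ER visits. Section 9.0 already provides a HIPAA waiver for administrative follow-up data. Show events learned of only through counseling calls in a separate column.

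The cost is a wording amendment, a log, more background hospitalizations for the PI to review (most needing one line), and a small addition to the survey or EMR extract.
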